## 4. INTRODUCTION

This Statistical Analysis Plan (SAP) describes the planned analysis and reporting of data collected from MorphoSys protocol MOR202C103, Version 7.0, dated 07-Jul-2020. Any amendments to the protocol, which do not affect the statistical aspects of the trial will not necessitate a SAP update.

This study is a two-cohort, non-randomized, open-label, multicenter clinical trial to assess safety and efficacy of the human anti-CD38 antibody MOR202 in anti-PLA2R antibody positive membranous nephropathy (aMN) subjects eligible for immunosuppressive therapy (IST) or who have failed to respond to previous IST. The structure and content of this SAP are specified to give detailed and comprehensive description of the endpoints in the study and the corresponding analyses in accordance with the requirements identified by the Food and Drug Administration (FDA), European Medicines Agency (EMA), and International Conference on Harmonization (ICH) of Technical Requirements for Registration of Pharmaceuticals for Human Use: Guidance on Statistical Principles in Clinical Trials. All work planned and reported from this SAP will follow internationally accepted guidelines, published by the American Statistical Association and the Royal Statistical Society, for statistical practice.

The planned analyses identified in this SAP may be included in clinical study report (CSRs) and/or in relevant summary report documents (e.g. regulatory submissions, or future manuscripts). Also, *post-hoc* exploratory analyses not necessarily identified in this SAP may be performed to further examine study data and will not require updating the final SAP. Any post-hoc, or unplanned, exploratory analysis performed will be clearly identified as such and described in the final CSR.

The SAP is based on the following documents:

- Clinical Research Protocol MOR202C103
- ICH Guidance on Statistical Principles for Clinical Trials (E9)

The reader of this SAP is encouraged to also read the clinical protocol, and other identified documents, for details on the planned conduct of this study. Operational aspects related to collection and timing of planned clinical assessments are not repeated in this SAP unless relevant to the planned analysis.

## 5. STUDY OBJECTIVES AND ENDPOINTS

An overview of the study objectives and endpoints is depicted in Table 5-1.

**Table 5-1: Study objectives and endpoints**

Study objective	Endpoint	Analysis
Primary objective:	Primary endpoint:	
To assess the safety and tolerability of MOR202 treatment in subjects with anti-PLA2R antibody positive membranous nephropathy (aMN)	Incidence and severity of TEAEs	Section 11.1

**STATISTICAL ANALYSIS PLAN**

[figure not shown]
MorphoSys AG

MOR202C103

Study objective	Endpoint	Analysis
Key secondary objective:	Key secondary endpoint:	
To assess the effect of MOR202 on serum anti-PLA2R antibodies in subjects with aMN	Best Immunological response: rate of sICR, ICR and IPR based on reduction of serum anti-PLA2R antibody titer	Section 10.1
Secondary objectives:	Secondary endpoints:	
1. To assess immunogenicity of MOR202 (anti-MOR202 antibody formation) in subjects with aMN	Number and antibody titers of subjects tested positive for anti-MOR202 antibodies	Section 13
2. To assess the pharmacokinetic (PK) profile of MOR202 in subjects with aMN	MOR202 serum concentrations after multiple i.v. administrations	Section 12
3. To assess the safety in subjects with aMN after MOR202 treatment and during the follow-up phase.	Incidence and severity of adverse events (AEs) in the follow-up phase.	Section 11.1
Exploratory objectives:	Exploratory endpoints:	

CCI

Study objective	Endpoint	Analysis

CCI
 		

[figure not shown]
## 6. STUDY DESIGN

### 6.1. General study design

This phase Ib/IIa multicenter trial enrolls subjects with anti-PLA2R antibody positive membranous nephropathy (aMN) indicated for immunosuppressive therapy (IST) into two cohorts:

- Cohort 1 consists of approximately 20 aMN subjects newly diagnosed or relapsing subjects stable on supportive care treatment with ACEI/ARB at screening with proteinuria and medium/high serum titers of anti-PLA2R antibodies eligible for immunosuppressive therapy (IST).
- Cohort 2 consists of approximately 10 subjects with aMN refractory to IST and requiring other forms of IST.

The trial design includes a Safety Run-in, which in the initial stage of the trial intends to limit drug exposure to the first three subjects. All trial subjects, including the safety run-in subjects, will follow the clinical trial schedule in Figure 6-1. Each treatment cycle (C) consists of 28 days (D).

**Figure 6-1 Clinical Trial Schedule**

Please refer to section 6.2 of the clinical trial protocol for more details on the screening phase, treatment phase and follow-up phase.

## 6.2. Schedule of assessments

Please refer to section 10 of the clinical trial protocol for the full schedule of assessments.

## 6.3. Determination of sample size

As this is a Phase Ib/IIa trial primarily conducted to explore safety endpoints, no formal statistical hypothesis has been established for the sample size calculation of this trial.

Three evaluable subjects will be enrolled in the safety run-in phase. These subjects can belong to either Cohort 1 or Cohort 2.

Once the safety run-in is completed successfully, additional subjects will be enrolled in Cohort 1 and Cohort 2 in parallel. Approximately 20 subjects will be enrolled in Cohort 1 and approximately 10 subjects will be enrolled in Cohort 2.

With a sample size of 20 subjects in Cohort 1, there is an 88% probability to observe at least one occurrence of a particular adverse event if the natural incidence of this adverse event in Cohort 1 is 10%.

Cohort 2 includes subjects refractory to IST with up to 2 prior lines of treatment. Thus it is expected that incidence of AEs will be higher in Cohort 2 than in Cohort 1. With a sample size of 10 subjects in Cohort 2, there is a 80% probability to observe at least one occurrence of a particular adverse event if the incidence of this adverse event is 15%.

---

## 6.4. Timing of analyses

### 6.4.1. Safety run-in analyses

The first three subjects dosed in this trial (regardless of cohort) will be treated and observed until Cycle 2 Day 1 or until having demonstrated a toxicity leading to discontinuation of treatment, whichever is earlier. If a grade 4/5 adverse drug reaction (ADR) occurs during the safety run-in, then a safety review will take place and start of treatment for further subjects will be contingent on safety review outcome.

The safety review will consist of an evaluation based on the number and type of all AEs occurring during the first cycle and laboratory values (biochemistry and hematology) and will be performed by representatives of the Safety Review Panel consisting of representatives of the participating investigators and the sponsor. The safety review will be held after C2D1 of the 3rd subject. For more details refer to section 6.3 of the clinical trial protocol.

### 6.4.2. Primary completion analysis

The primary completion analysis will be performed after the last subject completes Cycle 6 of treatment (after the EOT visit), or 28 days after the last subject received the last dose of MOR202 (only for early termination).

If the enrolment for one of the cohorts is significantly longer (approximately two months difference between the enrolment of the last subject in Cohort 1 and the last subject in Cohort 2), the Primary Completion Analysis may be performed by cohort. In this case, no overall summary of both cohorts will be presented in the analysis. Otherwise the analyses will be performed for both cohorts at the same time.

Primary, key secondary and selected exploratory endpoints will be analysed at the time of Primary Completion. For more details, see Table 8-1 in section 8.4.

### 6.4.3. Final analysis

The final analysis will be performed after all subjects completed either their EOS visit or completed the “*Early study discontinuation*” eCRF page.

## 7. DEFINITIONS AND GENERAL METHODOLOGY

### 7.1. Treatment cycle

The subjects will be administered study treatment according to cycles. Each treatment cycle (C) consists of 28 days (D).

The planned administration of MOR202 is as follows:

Cycle 1: Day 1, Day 8, Day 15, Day 22

Cycle 2 to Cycle 6: Day 1

---

## 7.2. Study drug/treatment

Study drug and study treatment refer to the individual drug MOR202. In the rest of the SAP we will refer to it only as “study drug”.

## 7.3. Study drug administration

### 7.3.1. Date of first administration of study drug

The date of first administration of study drug for a subject is the first date when a non-zero dose of study drug is administered and is referred to as “start date of study drug”.

### 7.3.2. Date of last administration of study drug

The date of last administration of study drug for a subject is the last date when a non-zero dose of study drug is administered and is referred to as “end date of study drug”.

## 7.4. Reference start date and study day

The reference start date will be defined as the start date of study drug for all

Safety assessments (e.g. adverse event onset, laboratory abnormality occurrence, etc.)

Efficacy assessments (e.g. response assessments, etc.)

Non-safety screening assessments, baseline disease characteristics, medical history that occurred prior to start date of study treatment

The study day describes the day of the event or assessment, relative to the reference start date. The reference start date is designated as Study Day 1. Study Day -1 is the day that precedes Study Day 1. Study Day 0 is not defined.

The study day will be calculated as:

The date of the event (visit date, assessment date, etc.) – reference start date + 1 day, if the event is on or after the reference start date

The date of the event (visit date, assessment date, etc.) – reference start date, if the event precedes the reference start date

The study day will be displayed in the data listings.

## 7.5. Screening failure

Screening failures are subjects who have signed informed consent and failed screening criteria. Subjects who signed informed consent and fulfilled screening criteria, but have never received treatment are not considered as screening failures. These subjects are referred to as “Not treated subjects”.

## 7.6. Time unit

A month-length is 30.4375 days (365.25/12). If duration is to be reported in months, duration in days is divided by 30.4375. If duration is to be reported in years, duration in days will be divided by 365.25.

## 7.7. Baseline

Baseline is the result of an investigation describing the “true” uninfluenced state of the subject, defined as the period from the date of signing any informed consent document to the start date of study drug.

Unless otherwise stated in the respective sections, the last non-missing assessment, including unscheduled assessments, on or before the start date of study drug prior to the first dosing of the study drug will be used as “baseline” value or “baseline” assessment. Assessments collected post-dose on the first date of treatment are not considered as baseline values.

Baseline values for proteinuria responses are defined in the respective section.

If a subject has no value as defined above, the baseline value will be considered as missing.

Data listings will include baseline flags.

### Change from baseline calculation

Absolute change from baseline will be calculated as

$$[\text{visit value} - \text{baseline value}]$$

and percentage change from baseline will be calculated as

$$\left[ \frac{\text{visit value} - \text{baseline value}}{\text{baseline value}} \times 100 \right].$$

## 7.8. On treatment assessment/event

### On-treatment assessment/event

An on-treatment assessment/event is defined as any assessment/event happening after the start date of study treatment, i.e. assessments/events happening in the following time interval (including the lower and upper limits):

[Start date of study drug +1 day; End date of study drug + 28 days].

Assessments collected post-dose on the start date of study drug are also considered as on-treatment assessments. Data listings will include all assessments/events, flagging those which are not on-treatment assessments/events.

### Post-treatment assessment/event

A post-treatment assessment/event is defined as any assessment happening after the completion of the on-treatment phase, i.e. assessments/events happening in the following time interval (including the lower and upper limits):

[End date of study drug + 28 days + 1 day; Date of study discontinuation].

The date of study discontinuation is defined as the date of the End of Study Visit, or the date entered in the “*Early study discontinuation*” eCRF page, whichever is later.

## 7.9. End of treatment

End of treatment (EOT) is defined as the assessment obtained on the EOT visit date.

Change from EOT will be calculated similarly to change from baseline as described in section 7.7, replacing baseline value with the value obtained at EOT.

## 7.10. Analysis visits

For parameters that will be summarized by visit, the nominal visit as recorded in the eCRF (i.e. actual visit date) will be used (disregarding the allowed assessment windows). Data collected in unscheduled visits will be displayed in patient data listings and spaghetti plots only, except Baseline assessment (refer to section 7.7). The unscheduled visit results will be flagged in the listings accordingly and will be highlighted by asterisks on spaghetti plots.

In the case of multiple records for one visit, selection rules are described in section 7.11 (below).

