### 3. LIST OF ABBREVIATIONS AND DEFINITIONS OF TERMS

#### 3.1. List of Abbreviations

ACEI	Angiotensin Converting Enzyme Inhibitor
ACTH	Adrenocorticotrophic hormone
ADA	Anti drug antibody
ADCC	antibody-dependent cell-mediated cytotoxicity
ADCP	antibody-dependent cell-mediated phagocytosis
ADR	Adverse drug reaction
AE	Adverse event, for definition see 10.8.6
AESI	Adverse Event of Special Interest
ALT	Alanine-Aminotransferase
aMN	Anti-PLA2R antibody positive membranous nephropathy
Anti-PLA2R	Anti phospholipase A2 receptor antibodies
ANSM	Agence Nationale de Sécurité du Médicament et des Produits de Santé
ARB	Angiotensin II Receptor Blocker
AST	aspartate aminotransferase
ATC	Anatomical Therapeutic Chemical Classification
AUC	Area under the curve
BAFF	B-Cell Activating Factor
β-hCG	β human Chorionic Gonadotropin
BIR	best overall immunological response
BIRR	best overall immunological response rate
BL	Baseline
BP	Blood pressure
BPR	Best proteinuria response
CBC	Complete blood cell count
CD	Cluster of differentiation
CD20	B-lymphocyte antigen CD20
CD38	B-lymphocyte antigen CD38
C max	Maximum concentration
CI	Confidence Interval
CNI	Calcineurin inhibitor

CKD-EPI	Chronic Kidney Disease Epidemiology Collaboration
CR	Complete response
CRF	Case Report Form
CRO	Contract research organization
CSA	Cyclosporin A
C trough	Minimum concentration
CTFG	Clinical Trial Facilitation Group
CX	Various fractions of complement, C1q, C5a, ....
CXDY	Cycle X Day Y (eg C1D1 is the 1 st day of the 1 st cycle)
DEX	Dexamethasone
DMC	Data Monitoring Committee
DTT	Dithiothreitol
ECG	Electrocardiogram
eCRF	Electronic Case Report Form
EDTA	Ethylenediaminetetraacetic acid
eGFR	estimated glomerular filtration rate
ELISA	Enzyme-linked immunosorbent assay
EOS	End of study visit (28 weeks after EOT)
EOT	End of therapy visit (28 days after last dose)
ESA	Erythropoiesis stimulating agent
ESRD	End stage renal disease
EudraCT	European Union Drug Regulating Authorities Clinical Trials
FAS	Full analysis set
FCBP	Female of childbearing potential
FDA	Food and Drug Administration
FiH	First in Human
FSH	Follicle stimulating hormone
FUV	Follow up visit (14 weeks after EOT)
GCP	Good Clinical Practice
GFR	Glomerular Filtration Rate
GGT	Gamma-Glutamyltransferase
Hba 1c	Glycated hemoglobin

HBcAg	Hepatitis B core antigen
HBsAb	Hepatitis B surface antibody
HBsAg	Hepatitis B surface antigen
HCV	Hepatitis C virus
HIV	Human Immunodeficiency Virus

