## **8.8. Subject Discontinuation of IMP and Subject Withdrawal**

### **8.8.1. Discontinuation due to toxicity**

MOR202 treatment must be permanently discontinued, if:

- Needing platelet transfusion.
- Not recovering to  $\leq$  grade 2 from  $\geq$  grade 3 ADRs related to MOR202 within 21 days despite adequate treatment of the ADR.
- Experiencing grade 4 IRR.

Subjects discontinuing MOR202 treatment will have their EOT visit (earliest after 28 days after last dose of MOR202) and enter the follow-up phase.

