### **8.8.2. Discontinuation due to other reasons**

MOR202 treatment must be permanently discontinued for subjects:

- With progressive disease as defined in [Section 3.2](#)
- Wishing to discontinue MOR202 treatment
- With pregnancy

Investigator(s) have the right to discontinue subjects from MOR202 treatment in the event of illness, AEs, or other reasons putting a risk to the health or well-being of the subject, or in case of lack of subject's co-operation.

The reason for discontinuing MOR202 treatment must be noted in the eCRF.

Subjects discontinuing MOR202 treatment will have their EOT visit (earliest after 28 days after last dose of MOR202) and enter the follow-up phase.

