#### Main Analysis

The main analysis will be conducted on FAS. The following information will be presented by cohort and overall:

- Number (%) of subjects achieving a BIR of IPR at any time during the trial
- Number (%) of subjects achieving a BIR of ICR at any time during the trial
- Number (%) of subjects achieving a BIR of sICR at any time during the trial
- BIRR along with the 95% confidence interval (CI, using the Clopper-Pearson exact method)
- Number (%) of subjects with a BIR of PD at any time during the trial
- Number (%) of subjects classified as Non-responder

For each visit available, the number and percentages of subjects in each of the response categories will be tabulated, including missing response evaluations and subjects with a progressive disease. Subjects, who are not classified in either response category or progressive disease will be tabulated as “*Non-Responders*”. Subjects with no post-baseline assessment of response will be included as “*Non-Responders*”.

If a subject achieves several responses, the subject will be tabulated in the highest achieved response category.

No formal hypothesis testing will be conducted.

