## 10.2. Analysis of 24 hour urine

24 hour urine will be collected to assess the following parameters:

- Urine protein
- Urine creatinine
- Urine sodium
- CCI [REDACTED]

The following information will be summarized for each 24 hour urine parameter above by cohort and overall on FAS:

Absolute levels by visit

Absolute and percentage change from baseline to each visit until end of study

Listings with individual urine parameter levels will be generated by visit on FAS.

- The following plots will be generated by cohort on FAS for UPCR and Urine creatinine:
  - Spaghetti plots (time vs. parameter value for each subject)
  - Spaghetti plots (time starting from baseline vs. % change from baseline for each subject) – please add dotted reference lines for upper (50%) and lower (-50%) thresholds.
  - Waterfall plot for relative change from baseline at EOT, FUV and EOS – please add study days under the corresponding subject IDs

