### 10.10. Sensitivity analysis

The sensitivity analysis will be performed on the FAS excluding subjects who received  $\leq 70\%$  of the MOR202 doses overall (please see section 9.6.5 for the details) or who received at least one dose of relevant IST therapies at any timepoint of the study in accordance with the visit windows defined in Table 3. The relevant IST therapies will be identified on a case-by-case basis by a medical review of the concomitant medication listing (please refer to section 7.13.6 for the details) and documented in the data review meeting minutes.

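### By-visit efficacy summaries pool early stoppers with completers seen 28 to 140 days later, and the only day-based analysis is run after dose and IST exclusions

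*SAP*

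**What the plan says.** SAP 7.10 assigns data to visits by the eCRF label, which "will be used (disregarding the allowed assessment windows". Two legible sets of efficacy outputs use that rule.

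- SAP 10.1: "For each visit available, the number and percentages of subjects in each of the response categories will be tabulated".
- SAP 10.2, 24-hour urine: "Absolute and percentage change from baseline to each visit until end of study", with waterfall plots at EOT, FUV and EOS.

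Under Protocol 8.8.1, subjects stopped for toxicity "will have their EOT visit (earliest after 28 days after last dose of MOR202) and enter the follow-up phase". Protocol 8.8.2 says the same for other reasons: "Subjects discontinuing MOR202 treatment will have their EOT visit (earliest after 28 days after last dose of MOR202) and enter the follow-up phase". Later visits are counted from EOT: FUV is defined as "Follow up visit (14 weeks after EOT" weeks' interval and EOS follows 28 weeks after EOT. Protocol Table 2 puts a completer's EOT, FUV and EOS on Days 169, 267 and 366.

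Day-based windows appear only in SAP 10.10, Table 3. That section opens: "The sensitivity analysis will be performed on the FAS excluding subjects who received" 70% or less of their MOR202 doses overall. It also drops anyone given a relevant IST, and ties the windows to what remains. SAP 9.6.5 defines overall compliance as the sum of actual doses over the sum of planned doses. It does not say whether doses after a permanent stop count as planned.

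**The concern.** One label covers different times since treatment start. A row headed EOT mixes completers at about six months with early stoppers who may be at one to four months, and FUV and EOS inherit the same shift. After baseline, 24-hour urine is collected only at C4D1, EOT, FUV and EOS, so three of its four post-baseline visits are exposed. Stopping is also informative, because progressive disease is itself a reason for stopping under Protocol 8.8.2.

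The plan holds the tool to examine this, but couples it to two subject exclusions. If the windowed result differed from the main one, nobody could say whether the cause was timing, low exposure or IST. The SAP's document history (version 6.0) gives the purpose of the windows as assigning data by calendar day without losing subjects' data. Removing subjects first works against that purpose.

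**Working it through.** **Inputs.** Nine planned doses on Days 1, 8, 15, 22, 29, 57, 85, 113 and 141 (Protocol 6.5 and Table 2). Earliest EOT = last dose day + 28. FUV = EOT + 98. EOS = EOT + 196. The exclusion cut-off is 70% or less (SAP 9.6.5 and 10.10). The six-month window is Day 139 to Day 229 (SAP Table 3).

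**The plan's own figures.** For a completer, 141 + 28 = 169; 169 + 98 = 267; 169 + 196 = 365. Protocol Table 2 gives 169, 267 and 366, so the schedule is reproduced to within one day at EOS.

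**Early stoppers**, at the earliest permitted dates and with nine doses as the assumed denominator:

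| Last dose received | EOT / FUV / EOS day | EOT days before a completer's | Share of 9 doses | SAP 10.10 | Table 3 window of EOT |
|---|---|---|---|---|---|
| 1 | 29 / 127 / 225 | 140 | 11.1% | excluded | 1 month |
| 2 | 36 / 134 / 232 | 133 | 22.2% | excluded | 1 month |
| 3 | 43 / 141 / 239 | 126 | 33.3% | excluded | 1 month |
| 4 | 50 / 148 / 246 | 119 | 44.4% | excluded | 2 months |
| 5 | 57 / 155 / 253 | 112 | 55.6% | excluded | 2 months |
| 6 | 85 / 183 / 281 | 84 | 66.7% | excluded | 3 months |
| 7 | 113 / 211 / 309 | 56 | 77.8% | kept | 4 months |
| 8 | 141 / 239 / 337 | 28 | 88.9% | kept | 6 months |

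A dose-1 stopper's EOS (Day 225) comes before a completer's FUV (Day 267).

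**What the windows would move.** On the full FAS they would take the EOT of stoppers after doses 1 to 7 out of the completers' six-month window. With the exclusions, only dose-7 stoppers are both kept and moved. Six of the seven stopping points (6/7 = 86%) are lost, and they carry the six largest shifts (84 to 140 days).

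**Share of subjects rather than of stopping points.** The documents give no distribution of stopping times. If stopping were uniform from Day 1 to Day 141 (an assumption), (85 − 1)/(141 − 1) = 84/140 = 60% of early stoppers would be excluded, and 84/(113 − 1) = 84/112 = 75% of those whose EOT would move. The excluded would cease to be the majority only if at least half of the movable stoppers stopped after exactly dose 7.

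**Other denominator.** If planned doses count only up to the stop, a subject who received every dose until then has 100% compliance and is not excluded on dose.

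**Number of subjects.** The protocol synopsis expects about 10% to leave the trial before the end of the last cycle: 0.10 × 30 = 3. At an assumed 20% to 30% it would be 6 to 9. One subject weighs 1/20 = 5 percentage points in Cohort 1 and 1/10 = 10 in Cohort 2. That is a weight, not an estimate of bias.

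**The case against.** The strongest reply is that EOT is defined relative to the last dose. A row at a fixed interval after last dose is a legitimate summary, and preferring calendar alignment is partly a matter of choice. This stands, and is why the main tables need not be relabelled.

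Several limits on scope also stand.

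- A reader might infer that the trial's main results are distorted. They are not: TEAEs are anchored to the dosing dates, the best immunological response rate counts a response whenever it occurs, and "No formal hypothesis testing will be conducted".
- A reader might infer that every early stopper is displaced. Subjects stopped for confirmed sICR keep their planned calendar (Protocol 8.8.3). Those who withdraw during treatment, or are withdrawn then for IST, do not enter follow-up (8.8.4, 8.8.5) and contribute an EOT at most.
- Timing is partly disclosed. Spaghetti plots use time, the SAP 10.2 waterfall plots print study days, and listings carry study day. This does not correct the tables.
- The windows are not a full cure. A dose-8 stopper's EOT (Day 141) stays in the completers' window. A dose-2 stopper seen on Days 36, 134 and 232 has no value in the six-month window.
- The 10% figure is for leaving the trial, whereas displaced FUV and EOS visits need subjects who stop treatment and stay in.

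**Conclusion.** The point holds for the descriptive by-visit efficacy summaries: immunological response categories by visit, and 24-hour urine changes at EOT, FUV and EOS. In these, subjects who stop MOR202 early for toxicity or other reasons and remain in the trial share rows with completers whose same-named visits fall 28 to 140 days later.

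The second half is conditional. It is tempting to say that everyone stopping after one to six doses is certainly removed from the windowed analysis. The documents do not settle that. SAP 10.10 refers to doses overall, which favors nine as the denominator, but SAP 9.6.5 leaves it open. With nine, the windowed analysis loses six of the seven stopping points it would re-map. With the other reading, the dose exclusion has little effect on early stoppers and only the IST exclusion remains tied to the windows.

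The number of displaced subjects is not given, and about 3 of 30 is only a proxy. SAP 10.3 to 10.9 and part of the endpoint list in 10.10 are blacked out, so a different visit rule there, or coverage of 24-hour urine, cannot be seen. This is a cheap improvement to a sensitivity analysis, not a threat to the primary or key secondary result.

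**What to change.** In SAP 10.10, split the analysis in two:

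1. Apply the Table 3 windows to the full FAS with no subject exclusions.
2. Run the dose and IST exclusions as a separate sensitivity analysis.

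In SAP 9.6.5, state whether the denominator of the 70% rule is all nine planned doses or only those planned up to a permanent stop.

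The cost is one additional set of sensitivity outputs from programs already planned; no new data are needed. Some early stoppers will have no value in certain windows, so each windowed table should show the number of subjects contributing.
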